5.4.2 Treatment of outlier data

In the case of outlier values, the secondary endpoint (lateral and angular deviations) should be assessed through statistical analysis using the actual values, as well as at least one other analysis after the outliers have been removed or their effect reduced.

An outlier search will be performed, and the actions to be taken will be determined in consultation with the Sponsor.

5.4.3 Treatment of incomplete and missing dates

No management of incomplete/missing dates will be performed for any pre-study events (all medical events or patient history that occurred before the start of the study, for example a previous fracture). Incomplete/missing dates will be labeled as such in all listings. However, for calculations, sorting, or assignments based on dates, the actions to be taken will be defined in consultation with the Sponsor.

6 - Statistical methods

6.1 Analysis methods

The statistical analyses will be based on the data from the different sites that participated in the study. The ICUREsearch statistics team will perform all statistical analyses.

Descriptive statistics for qualitative and quantitative variables and individual data listings will be generated.

6.1.1 Main analysis

The objective of this study is to evaluate the feasibility of the EPIONE robotic assistance for bone percutaneous procedures. The primary endpoint of this study is the successful insertion of the introducer with the assistance of the EPIONE device. Non-inferiority of the success rate of the EPIONE device, compared to the pre-clinical study (feasibility observed during pre-clinical tests), will be concluded if the lower bound of the one-sided 95% confidence interval for the observed proportion of successful EPIONE device uses is greater than or equal to 0.88 (0.96 minus a non-inferiority margin of 0.08).

A non-inferiority test for proportions will be conducted. The variable of interest is the success rate (proportion) of the introducer insertion with the assistance of the EPIONE device. The non-inferiority test will compare the success rate observed in the study with the reference value of 0.88.

The success rate will first be calculated, followed by the computation of a one-sided 95% confidence interval for this proportion. Non-inferiority will be concluded if the lower bound of the 95% confidence interval for the success rate is greater than or equal to 0.88.

Null hypothesis (H0): The success rate is less than 0.88.

Alternative hypothesis (H1): The success rate is greater than or equal to 0.88 (non-inferiority).

The frequency and percentage of successful introducer insertions with EPIONE device assistance will be reported.

This analysis will be conducted on the mITT population.

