Eligibility criteria / Critères d'éligibilité	
Inclusion criteria
 
• Patient ≥ 18 years,• Patient approved for CT-guided percutaneous bone procedure under general anaesthesia at a multidisciplinary consultation meeting,• Patient who has signed an informed consent form,• Patient covered by a social security system• Patient who has already been included in the EPIBONE study for one or more given musculoskeletal disorders and for whom a new location is targeted for a CT-guided procedure that can be assisted again by the EPIONE device. 
Exclusion criteria
 
• Patient unable to undergo general anaesthesia,• Patient offered a procedure without appropriate breathing control,• Patient approved for CT-guided percutaneous procedures on head and neck, including skull and cervical vertebrae• Patient unable to fully understand all relevant aspects of the clinical study necessary for his/her decision to participate, or who could be manipulated or unduly influenced as a result of a compromised position, expectation of benefits or fear of retaliatory response• Pregnant or breast-feeding women,• Patient subject to a legal protection measure,• Patient already participating in another interventional clinical study,

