Study flowchart / Organigramme de l'étude	
The diagram illustrates the study timeline. It starts with a 'Pre-intervention consultation' leading to 'Visit 0' (V0=D0). This is followed by an 'Inclusion visit' and the 'Day of the intervention'. After 'Visit 0', the timeline continues to 'Visit 1' (D0+3w ≤ V1 ≤ D0+8w), which includes a 'Follow-up visit' and a 'Post-intervention visit'.

	
The interventional radiologist will explain to the patient the planned procedure(s) and will present the response plan and its different steps during a pre-intervention consultation. The investigator:
 
 - will present the study and the device to the patient (oral and written information), - will review the inclusion and non-inclusion criteria of the study, and assess the patient's eligibility for the study, - Will provide the information letter and informed consent form to the patient, who must be able to read them and have time to think about his or her potential participation in the study prior to consent. - 
Demographics/medical data prior the intervention will be collected the day of the intervention if the patient returns a signed consent form and the investigator confirms the eligibility criteria. No data will be collected while prior intervention consultation, before signature of the written consentment.

Sample size / Taille de l'échantillon	
The size of the sample of at least 67 insertions was calculated to assess the non-inferiority of the successful insertion rate of the introducer (with the help of EPIONE), using a reference proportion of 96% and with a non-inferiority threshold of 0.08 under the assumption of 97% of feasibility for the study.
 
In line with centers practice, that is to say an average of 2 insertions per patient (different locations of possible musculoskeletal disorders, different possible treatments during the same procedure), it is planned to include a minimum of 34 patients in this study.

Randomisation and blinding / Randomisation et aveugle	
Not applicable.

Investigation Number: EPIBONE

ClinicalTrials.gov ID:

CIV-ID: 2024-A00468-39

Document title: EPIBONE Clinical Investigation Synopsis

Doc No: CA-BO-SYN-0053

Revision: B

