Statistical methods / Méthode statistiques	
analysis d'analyses
 
The statistical analysis will be performed at risk 0.05 and a power of 80%. The outcome of the primary endpoint will be assessed by a non-inferiority test compared to the results of the preclinical study.
 
The primary endpoint analysis will be performed on the mITT population (modified Intention to Treat population). The security analysis will be carried out on the security population.
 
A statistical analysis plan will be drafted and validated before the database is locked. Quantitative variables will be described using frequencies of missing and non-missing data, means, standard deviations, medians, quartiles, minimums and maximums. Qualitative variables will be described using the frequency of non-missing and of shortages, frequency and percentage by modality

Study duration per patient / Durée de l'étude par patient	
The average duration of a patient's participation in the study is 1 month. The patient's participation will be of a minimum of 3 weeks or a maximum of 8 weeks.

Study schedule / Agenda de l'étude	
Inclusion start time: Beginning of Q3 2024 Inclusion period: 6 months End of study visit of the last patient: end of Q1 2025/ Beginning of Q2 2025.

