3.2.1 Sample size

The sample size calculation was performed based on a one-sample non-inferiority test design. The preclinical study showed that 96% of insertions assisted with the EPIONE device were successful. Assuming 97% feasibility with EPIONE system, with a clinically acceptable margin of 0.08, the sample size necessary to achieve 90% power and maintain the type I error rate at 5% for this non-inferiority margin was calculated to be approximately 67 insertions.

[figure not shown]
The sample size was calculated using the Cohen's arcsine transformation, which is a preferred method when dealing with proportions close to the boundaries (0 or 1) as it helps to stabilize the variance and normalize the data.

Considering the practice of the centers, i.e. an average of 2 introducer insertions per patient (different locations of MSK disorders possible, different treatments possible during the same procedure), it is planned to include a minimum of 34 patients in the study.

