5.2 Statistical tests

All tests other than the non-inferiority test of the primary endpoint will be two-sided with a global alpha risk level of 5%. A p-value less than 0.05 will be considered statistically significant. All confidence intervals will be two-sided and presented with a 95% confidence level.

The non-inferiority test of the primary criterion will be one-sided with a global alpha risk level of 5%. A p-value less than 0.05 will be considered statistically significant. Confidence interval will be one-sided and presented with a 95% confidence level.

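### The 90% power and 5% error stated for 67 insertions belong to a planning formula, not to the primary decision rule, whose interval is not named

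*SAP*

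**What the plan says.** SAP 6.1.1 makes the insertion the unit of the primary analysis: "The variable of interest is the success rate (proportion) of the introducer insertion with the assistance of the EPIONE device". Success is concluded if the lower limit of a one-sided 95% interval is at least 0.88, that is, 0.96 minus a margin of 0.08. SAP 5.2 adds only level and sidedness: "Confidence interval will be one-sided and presented with a 95% confidence level". Neither section says how the interval is computed.

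SAP 3.2.1 gives about 67 insertions as "the sample size necessary to achieve 90% power and maintain the type I error rate at 5" per cent. It names Cohen's arcsine transformation, but only for the sample size. It then divides by "an average of 2 introducer insertions per patient (different locations of MSK disorders possible, different treatments possible during the same procedure" to reach at least 34 patients.

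The Protocol synopsis has the same count, "The size of the sample of at least 67 insertions was calculated", but a different power: "The statistical analysis will be performed at risk 0.05 and a power of 80" per cent.

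The passages available give no intra-patient correlation, design effect or clustered analysis. The full clinical investigation plan, the figure in SAP 3.2.1 and SAP section 9 are not available, so the point is limited to the text that is.

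**The concern.** The SAP calls the study pivotal, and its one confirmatory conclusion turns on whether a lower bound clears 0.88. With about 2 failures expected among 67 or 68 insertions (3% of 68 is 2.04), a single failure can decide the result. Common intervals differ by exactly one failure in what they allow. If the method is not fixed before the data are known, the rule, its type I error and its power are not fixed either. The figures in 3.2.1 then describe a calculation that is not tied to the test in 6.1.1.

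Insertions are also expected to come about two to a patient. The planning formula treats them as independent and the text does not say so. If failures tend to occur together in a patient, the true type I error is higher than the independent calculation shows.

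**Working it through.** **Inputs.** Null threshold 0.88 (SAP 6.1.1); assumed true rate 0.97, power 90% and type I error 5% (SAP 3.2.1); one-sided test (SAP 5.2); an average of 2 insertions per patient and at least 34 patients (SAP 3.2.1), so 34 × 2 = 68 insertions.

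**1. The plan's own figure.** Effect size h = 2·asin(√0.97) − 2·asin(√0.88) = 0.3593. Then n = ((1.645 + 1.282)/h)² = 66.33, rounded up to 67. The figure reproduces. With 80% power the same formula gives 47.89, so 67 goes with the SAP's 90% and not with the Protocol's 80%.

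**2. The rule in 6.1.1.** One-sided 95% lower bounds by number of failures:

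| Interval | 67, 3 failures | 67, 4 failures | 68, 3 failures | 68, 4 failures |
|---|---|---|---|---|
| Exact | 0.888 | 0.869 | 0.890 | 0.870 |
| Wilson | 0.893 | 0.874 | 0.895 | 0.875 |
| Wald | 0.914 | 0.893 | 0.915 | 0.894 |
| Arcsine | 0.905 | 0.884 | 0.906 | 0.886 |

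Three failures clear 0.88 under all four. Four failures fail under exact and Wilson and pass under Wald and arcsine.

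**3. Operating characteristics, independent insertions.** With F the number of failures, type I error is P(F ≤ c) with F ~ Bin(n, 0.12), and power is P(F ≤ c) with F ~ Bin(n, 0.03).

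| Rule | n | Type I error | Power |
|---|---|---|---|
| At most 3 failures (exact, Wilson) | 67 | 3.3% | 86% |
| At most 3 failures (exact, Wilson) | 68 | 3.0% | 85% |
| At most 4 failures (Wald, arcsine) | 67 | 8.3% | 95% |
| At most 4 failures (Wald, arcsine) | 68 | 7.7% | 95% |

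The first rule misses 90% power and the second exceeds 5% error. Moving the cut-off further in either direction makes the missed figure worse, so no cut-off at 67 or 68 gives both.

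**4. Dependence on n.** The exact bound has power 82% to 86% over 67 to 73 insertions. At 74 it allows a fourth failure and power is about 93%.

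**5. Clustering, conditional on an assumed ICC.** This uses the exact rule (at most 3 failures) at 68 insertions from 34 patients. For pairs, P(both fail) = q² + ICC·q(1−q), where q is the failure rate, and this fixes the distribution. Unequal cluster sizes need a further assumption; a beta-binomial was used.

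| Spread of insertions | Type I error, ICC 0.3 | Type I error, ICC 0.5 | Power, ICC 0.5 |
|---|---|---|---|
| 34 pairs | 5.0% | 6.5% | 81% |
| 17 patients with 1, 17 with 3 | 6.0% | 8.2% | 80% |

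With 20 patients having 1, 4 having 2 and 10 having 4 (20 + 8 + 40 = 68), power at ICC 0.5 is 79.5%.

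**6. Sensitivity bound.** With f failures, the bound is the 5% quantile of Beta((n−f)/DEFF, f/DEFF + 1). Here DEFF = 1 + (m* − 1)·ICC and m* is the sum of squared cluster sizes divided by n. For 34 pairs (m* = 2) and 3 failures it is 0.885 / 0.881 / 0.876 / 0.868 at ICC 0.1 / 0.2 / 0.3 / 0.5. For the 1-and-3 split, m* = (17·1 + 17·9)/68 = 2.5, so DEFF at ICC 0.5 is 1.75, and the bound with 2 failures is 0.878.

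**The case against.** **The sample sizes are minimums.** The Protocol says at least 67 insertions, and both documents give 34 patients as a minimum. At 74 insertions the exact rule meets both stated figures. This stands: the shortfall is a statement about 67 to 73, and the restated power must carry its n. It does not rescue 3.2.1, which attaches 90% to about 67.

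**Clopper-Pearson is a preference.** Another method could be pre-specified with its error rates. This stands in part, since the defect is that none is named. But Wald and arcsine breach the SAP's own 5% at 67 and 68. Wilson matches the exact bound there, yet allows a fourth failure at 71 to 73, where P(F ≤ 4) at a 12% failure rate is still above 5%.

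**The method may be stated elsewhere.** It could be in the full plan, the missing figure or SAP section 9. That cannot be excluded; if so, 6.1.1 needs only to repeat it, and 3.2.1 still needs correcting.

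**Stronger readings that the documents do not support.**
- A reader might infer that 67 is a miscalculation. It is not; it reproduces under the SAP's formula.
- A reader might infer that ignored clustering is the main fault, or that more patients or an adjusted primary rule are required. No document gives an ICC or shows that failures cluster. The Protocol admits a "Patient who has already been included in the EPIBONE study for one or more given musculoskeletal disorders", but the SAP's inclusion criteria omit this, so it is only a possible further source of repeats.
- In the other direction, a reader might infer from equal pairs that clustering matters only with exactly 3 failures, or that 80% power always holds. The uneven splits above contradict both at ICC 0.5, and the plan gives only an average per patient.

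**Conclusion.** The point holds and should be fixed before database lock. SAP 3.2.1 states a power and error pair that the rule in 6.1.1 does not have at 67 or 68 insertions, even if all insertions are independent. Depending on the interval, the pair is about 3% error with 85% to 86% power, or about 8% error with 95% power. Four failures would give opposite primary conclusions. These figures rest only on the SAP's inputs and binomial arithmetic.

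The clustering component is secondary and conditional. Under the exact rule at 68 insertions, type I error reaches 5.0% to 6.0% at an assumed ICC of 0.3 and 6.5% to 8.2% at 0.5, for equal pairs and the 1-and-3 split respectively. Power at ICC 0.5 is about 79% to 81% over the three spreads examined. The ICC values and the spreads are assumptions. Clustering justifies a supportive analysis and clear reporting, not a redesign.

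**What to change.** **SAP 6.1.1.** Name the exact (Clopper-Pearson) one-sided 95% lower bound on insertions as the primary rule.

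**SAP 3.2.1.** State that 67 comes from the arcsine formula and assumes independent insertions. Restate the power of the exact rule as about 85% to 86% at 67 to 68 insertions (82% to 86% over 67 to 73; about 93% at 74). Reconcile this with the 80% in the Protocol synopsis.

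**Supportive sensitivity analysis, pre-specified before database lock.** Treat the patient as the cluster, with one identifier per person across any re-inclusion. Recompute the exact bound on n/DEFF at the observed rate, with DEFF = 1 + (m* − 1) × ICC, m* from the observed cluster sizes, and ICC 0.1, 0.2, 0.3 and 0.5. State that it does not change the primary decision. A range is used because about 2 expected failures cannot estimate an ICC. Report the number of patients with any failed insertion and with more than one.

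**Cost.** A few lines of text and code, with no extra enrolment. The stated power is less favourable, and at 67 to 68 insertions one fewer failure is allowed than under Wald or arcsine. The sensitivity bound can fall below 0.88 beside a positive primary result (for example, 3 failures in 34 pairs at ICC 0.3), and the report would have to explain that.

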6.1.2 Secondary analyses

6.1.2.1 Secondary endpoint n°1

The objective of this analysis is to evaluate the safety of the EPIONE robotic assistance for bone percutaneous procedures.

The number of adverse events (AEs) will be described overall, by intensity, severity, and relationship with the device on a descriptive table. The frequency and percentage of AEs, ADEs, SAEs, SADEs, minor and major complications along with the 95% confidence interval, will be presented.

This analysis will be conducted on the safety population.

6.1.2.2 Secondary endpoint n°2

The objective of this analysis is to evaluate the accuracy of the EPIONE robotic assistance for bone percutaneous procedures.

A descriptive table displaying the mean lateral and angular deviations, based on expert review, will be provided.

This analysis will be conducted on the mITT and PP populations.

7 - Computer systems, software and program validation

7.1 System

The analyses will be conducted by a biostatistician from ICUREsearch. All analyses will be performed using Microsoft® Windows 11®.

7.2 Software

The analyses will be performed using SAS® software version 9.4. ICUREsearch reserves the right to use R® (CRAN) software for graphical representations.

7.3 Program validation

The biostatistician will be responsible for reviewing each program and the associated SAS® output. The SAS® "Log" will be saved and examined for logical errors, syntax issues, and fatal errors.

The raw results of the statistical analysis will be directly generated by the SAS software in the form of TLF (Tables, Listings, and Figures) in pdf format.

The results will be checked for typographical errors, spelling mistakes, and implausible values. The consistency of the results will be reviewed with the principal investigator.

8 - Conventions

8.1 Data formats and rules

8.2 Report

All sections of tables, figures, and listings are detailed in Section 9.4. They will be prepared using SAS® software (SAS Institute Inc., Cary, NC, USA) as PDF files (one PDF file per main section).

The footers will be presented as follows: "ICUREsearch SAS – CONFIDENTIAL."

List of page and table configuration requirements:

- Font type = Calibri
- Font size = 8 pt (minimum)
- Paper size = A4 (21 cm x 29.7 cm)
- Page orientation: portrait or landscape as needed
- Graphics: PNG or JPG format

[figure not shown]
The statistics will be presented as follows:

Parameter	Statistics / Category	Value
Gender	N	XX
	n Missing	XX XX
	Male, n (%)	XX (XX.X)
	Female, n (%)	XX (XX.X)
Height (cm)	N	XX
	n Missing	XX XX
	Mean (std)	XX (XX.X)
	Median [IQR]	XX [XX ; XX]
	Min ; Max	XX ; XX

Parameter	Statistics / Category	All	Cluster 1	Cluster 2	Pvalue
XXXX	N	XX	XX	XX	X.XXXX
	n Missing	XX XX	XX XX	XX XX	
	Mean (std)	XX (XX)	XX (XX)	XX (XX)	
	Median [IQR]	XX [XX ; XX]	XX [XX ; XX]	XX [XX ; XX]	
	Min ; Max	XX ; XX	XX ; XX	XX ; XX	
XXXX	N	XX	XX	XX	X.XXXX

Parameter	Statistics / Category	All	Cluster 1	Cluster 2	Pvalue
n Missing		XX XX	XX XX		
Mean (std)		XX (XX)	XX (XX)		
Median [IQR]		XX [XX ; XX]	XX [XX ; XX]		
Min ; Max		XX ; XX	XX ; XX		

The boxplots will be presented as follows:

An individual is considered an outlier when their value is less than 1.5 times the interquartile range (IQR) below Q1 and more than 1.5 times the IQR above Q3. An individual is considered a far outlier when their value is less than 3 times the IQR below Q1 and more than 3 times the IQR above Q3.

Example: We want to represent the boxplot of the individuals' heights in our population. The first quartile (Q1) is 160 cm, the median is 170 cm, and the third quartile (Q3) is 180 cm. The interquartile range is $Q3 - Q1 = 180 - 160 = 20$.

$$1.5 * 20 = 30, Q3 + 30 = 180 + 30 = 210 \text{ cm}, Q1 - 30 = 160 - 30 = 130 \text{ cm}.$$

So, if an individual is shorter than 130 cm or taller than 210 cm, they will be considered an outlier.

$$3 * 20 = 60, Q3 + 60 = 180 + 60 = 240 \text{ cm}, Q1 - 60 = 160 - 60 = 100 \text{ cm}.$$

Therefore, an individual will be considered a far outlier if they are shorter than 100 cm or taller than 240 cm.
